6.3.3. Immunogenicity Assessment

For the immunogenicity data, the percentage of patients with positive ADAs and neutralizing antibodies will be summarized by overall, tumor type, and dose within tumor type as data permit. For patients with positive ADAs, the magnitude (titer), time of onset, and duration of ADA response will also be described, if data permit. In addition, efforts will be made if data permit, as appropriate, to examine possible correlations of the ADA response with clinical data on the PK, safety and/or efficacy.

6.3.4. RO of PD-1 by PF-06801591 in Circulating T Cells

Descriptive statistics of PD-1 receptor occupancy by PF-06801591 evaluated from the percentage of free (ie unbound) PD-1 on the surface of circulating T cells will be summarized by overall, tumor type, and dose within tumor type as data permit.

CCI

6.5. Population PK and PK/PD Modeling

Pharmacokinetic and PD data from this study may be analyzed using modeling approaches and may also be pooled with data from other studies to investigate any association between PF-06801591 exposure and biomarkers or significant safety endpoints. The results of these analyses, if performed, may be reported separately.

6.6. ECG and Vital Sign Data Analysis

The analysis of ECG results will be based on patients in the Safety Analysis Set with baseline and on-treatment ECG data, and will follow the ICH E14 guidance on the clinical evaluation of QT/QTc interval prolongation and proarrhythmic potential for non-antiarrhythmic drugs.⁵

ECG measurements (an average of the triplicate measurements) will be used for the statistical analysis and all data presentations. Any data obtained from ECGs repeated for safety reasons after the nominal time-points will not be averaged along with the preceding triplicates.

Interval measurements from repeated ECGs will be included in the outlier analysis (categorical analysis) as individual values obtained at unscheduled time points.

QT intervals will be corrected for HR (QTc) using standard correction factors [ie, Fridericia's (default correction), Bazett's, and possibly a study specific factor, as appropriate]. QTcF interval will be calculated using the Friderica formula, as follows:

$$QTcF = \frac{QT}{\sqrt[5]{RR}}$$

Data will be summarized and listed for QT, HR, response rate (RR), PR, QRS, QTcF (and/or QTcB if deemed appropriate by overall, and dose. Individual QT' (all evaluated corrections) intervals will be listed by study arm time and dose. The most appropriate correction factor will be selected and used for the following analyses of central tendency and outliers and used for the study conclusions. Descriptive statistics (n, mean, median, standard deviation, minimum, and maximum) will be used to summarize the absolute corrected QT interval and changes from baseline in corrected QT after treatment by study arm dose and time point. For each patient and by treatment, the maximum change from baseline will be calculated as well as the maximum post-baseline interval across time points. Categorical analysis will be conducted for the maximum change from baseline in corrected QT and the maximum post- baseline QT interval.

Shift tables will be provided for baseline vs worst on treatment corrected QT (one or more correction methods will be used) using maximum CTCAE version 4.03 Grade. Shift tables will also be provided for ECG abnormality at baseline vs. on treatment (yes, no, not done: (n, %).

Patients experiencing clinically-relevant morphological ECG changes will be summarized (including frequency and percentage).

The effect of drug concentrations on corrected QT change from baseline may be explored graphically. Additional concentration-corrected QT analyses may be performed. Data may be pooled with other study results and/or explored further with PK/PD models.

Changes from baseline for the ECG parameters QT interval, heart rate (HR), QTc interval, PR interval and QRS interval will be summarized by treatment and visit. Categorical data analysis will follow [Appendix 9.3](#).

If more than one ECG is collected at a nominal time post dose (for example, triplicate ECGs), the mean of the replicate measurements will be used to represent a single observation at that time point. If any of the three individual ECG tracings has a QTc value ≥ 500 msec, but the mean of the triplicates is not ≥ 500 msec, the data from the subject's individual tracing will be described in a safety section of the study report in order to place the ≥ 500 msec value in appropriate clinical context. However, values from individual tracings within triplicate measurements that are ≥ 500 msec will not be included in the categorical analysis unless the average from the triplicate measurements is also ≥ 500 msec. Changes from baseline will be defined as the change between QTc post dose from the time-matched average of the pre-dose triplicate values on Day 1.

In addition, an attempt will be made to explore and characterize the relationship between plasma concentration and QT interval length using a PK/PD modeling approach. If a PK/PD relationship is found, the impact of subject factors (covariates) on the relationship will be examined.

7. INTERIM ANALYSES

There is no formal interim analysis planned in this study. In Part 2, a Bayesian approach will be used aiming to detect early sign of efficacy. The following analyses will be performed:

1. Approximately 8 weeks after the first 30 NSCLC patients have enrolled, a data snapshot will be taken for an early data assessment. Descriptive statistics (frequency and percentage) for tumor response (CR, PR, PD, stable disease [SD] etc.) from the first tumor assessment; ORR, the proportion of patients who achieved unconfirmed CR or PR, and the 95% confidence interval for ORR; DCR (disease control rate), the proportion of patients who achieved unconfirmed CR or PR or SD, and the 95% confidence interval for the DCR will be presented. If tumor response data are collected based on both RECIST 1.1 and irRECIST, separate presentations will be generated for each response criterion. In this data snapshot, some patients may have gone through their second tumor assessment as of the data snapshot, however only data through the first tumor assessment will be used for this analysis. The above described analyses may be repeated, if deemed necessary, when the first 40 or 45 NSCLC patients are enrolled and have gone through their first tumor assessment. This preliminary data may provide guidance in the decision to increase or decrease the sample size of each arm, to add other tumor types in a future amendment, or to initiate additional clinical studies.
2. In the early data assessment, a Bayesian approach will be used to calculate the posterior probability that the true ORR is greater than or equal to the minimal expected ORR. For example, the minimal expected ORR if all patients received only one tumor assessment is approximately 10% but may be adjusted based on how many patients had assessments beyond 8 weeks and the PD-L1 status of patients which will be tested at baseline. A beta prior (0.235, 1) is chosen, where the parameter beta is set to be 1, and parameter alpha 0.235 was calculated from a reference product pembrolizumab on NSCLC patients where a 19% ORR was observed. For example, if 4 responders are observed out of the first 30 patients as of the first tumor assessments, the posterior probability that the true ORR is greater than a minimal expected ORR of 10% is approximately 70%.

A final analysis will be performed when all 60 NSCLC patients and 40 urothelial cancer patients are enrolled and have completed their scheduled tumor assessments.

This is an open label study, the Pfizer study team will review safety, immunogenicity, pharmacodynamics, CCI [REDACTED] and other data throughout the study.

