Anti-tumor activity will be assessed through radiological tumor assessments conducted at baseline, during treatment as specified in the [Schedule Of Activities](#), whenever disease progression is suspected (eg, symptomatic deterioration), and at the time of withdrawal from treatment, if not done in the previous 3 weeks, after end of treatment for patients who did not end treatment due to disease progression, death, or withdrawal of consent, a tumor assessment will be performed every 12 weeks until disease progression by irRECIST, initiation of a new anti-cancer treatment, or end of trial (2 years after LPFD, see [Section 13.2](#)), whichever is first. Note: If a patient is classified as having PD during an on-treatment tumor assessment, then confirmation of PD by a second scan in the absence of rapid clinical deterioration is required per irRECIST.

CT or MRI scans to be done every 6 weeks (± 5 days) for patients on IV administration portion and every 8 weeks (± 5 days) for Parts 1 and 2 SC administration portion from the start of study entry (defined as C1D1) until disease progression by immune-related RECIST (irRECIST), death, withdraw consent, or subsequent administration of an anti-chemotherapy agent. CT or MRI scans may be assessed every 12 weeks (± 5 days) for patients who 1) have remained on treatment for ≥ 24 weeks, and 2) have no confirmed progression by irRECIST within the last 6 months, and 3) have demonstrated stability of disease. Tumor assessments should be fixed according to the calendar, regardless of treatment delays.

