2. In the early data assessment, a Bayesian approach will be used to calculate the posterior probability that the true ORR is greater than or equal to the minimal expected ORR. For example, the minimal expected ORR if all patients received only one tumor assessment is approximately 10% but may be adjusted based on how many patients had assessments beyond 8 weeks and the PD-L1 status of patients which will be tested at baseline. A beta prior (0.235, 1) is chosen, where the parameter beta is set to be 1, and parameter alpha 0.235 was calculated from a reference product pembrolizumab on NSCLC patients where a 19% ORR was observed. For example, if 4 responders are observed out of the first 30 patients as of the first tumor assessments, the posterior probability that the true ORR is greater than a minimal expected ORR of 10% is approximately 70%.

3. When all 70 NSCLC patients and 30 urothelial cancer patients are enrolled and have completed their scheduled tumor assessments, another snapshot will be taken. Descriptive statistics (frequency and percentage) will be presented for each tumor type (NSCLC or urothelial cancer) for the following endpoints:
 - Tumor response (CR, PR, PD, SD etc.) at each assessment;
 - Best overall response up to week 16 (ie, across the first two tumor assessments plus the next consecutive tumor assessment when a confirmatory scan is needed);
 - Best overall response across all assessments;
 - ORR, the proportion of patients who achieved CR or PR, by week 16 and the 95% confidence interval for ORR;
 - DCR (disease control rate), the proportion of patients who achieved CR or PR or SD, by week 16 and the 95% confidence interval for the DCR.

If tumor response data are collected based on both RECIST 1.1 and irRECIST, separate presentations will be generated for each response criterion.

Time to event data (overall survival [OS], progression-free survival [PFS], time to response [TTR], time to progression [TTP], DOR, and duration of stable disease [DOSD]) will be analyzed by the Kaplan-Meier approach for each tumor type.

The analyses may be separated and performed at two separate time points if the 70 NSCLC and 30 urothelial cancer patients do not complete enrollment at approximately the same time.

4. A final analysis will be performed at the end of the study, which will be 2 years from LPFD.

Detailed analyses for these efficacy endpoints will be described in the Statistical Analysis Plan (SAP).

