2. INTRODUCTION

This SAP provides the detailed methodology for summary and statistical analyses of the data collected in study B8011001. This document may modify the plans outlined in the protocol; however, any major modifications of the primary endpoint definition or its analysis will also be reflected in a protocol amendment. This SAP amendment is based on the protocol amendment 3 dated June 3, 2017.

Note: in this document any text taken directly from the protocol is *italicized*.

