5.5. Statistical Considerations of COVID-19 Impacted Data

In March 2020, prior to the database release for this study, the World Health Organization (WHO) announced a global pandemic of the virus SARS-CoV-2 and the resulting disease COVID-19. During the conduct of this trial, if any participant's data is impacted by this pandemic, the following considerations will be given in the data analyses:

- a. Death caused by COVID-19 is still considered as an "event" in the analysis of PFS (Parts 1 and 2) and OS (Part 2). If deemed necessary, a sensitivity analysis may be performed where COVID-19 driven death is censored at the death date.
- b. If a scheduled tumor radiographic scan is *delayed* out of the Schedule of Activity allowable window, or is *missing* (i.e. participant skipped a scheduled tumor radiographic scan) due to any reasons related to the pandemic, this delay or missingness does not alter the censoring rules for PFS or TTP. A censoring reason of "COVID-19" may be added to the PFS or TTP summary if the specific reason of tumor scan delay or missing can be attributed to COVID-19. If deemed necessary, a sensitivity analysis may be performed where participants would be censored on the date of COVID-19 diagnosis.

In the confirmed ORR analysis, as described in Section 6, if a response can't be confirmed by a subsequent tumor scan because of the pandemic (i.e. the subsequent tumor scan wasn't performed), then the initial response will be considered as unconfirmed. This is a conservative approach. No sensitivity analysis will be performed.

- c. Any COVID-19 related symptoms are to be captured as adverse events in the case report form. Those adverse events will be summarized in the same manner as other adverse events. If a label of COVID-19 can be identified in the investigator provided adverse event term, then a separate AE listing may be provided for just the COVID-19 related events.
- d. If identifiable, the COVID-19 related data points, including missing data where the reason of missing is identified as COVID-19 related (site closure hence data could not be captured; participants skipped a visit because of concern over the pandemic), protocol deviations driven by COVID-19, safety events caused by COVID-19 may be separately listed.

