6.2.3. ORR (Part 2)

ORR, as assessed using RECIST version 1.1 and irRECIST, is a primary efficacy endpoint for Part 2. The following analyses will be performed in the mITT population by tumor type (NSCLC or urothelial carcinoma) and pooled:

1. ORR by visit, separately for RECIST 1.1 and irRECIST: investigator provided tumor response CR, PR, and CR+PR will be presented by descriptive statistics (frequency and percentage) and 95% confidence interval.
2. Best overall response of CR, PR, and CR+PR, separately for RECIST 1.1 and irRECIST. This will include best overall response derivation without confirmation and with confirmation. Descriptive statistics (frequency and percentage) and 95% confidence interval will be provided.

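### SAP Amendment 2 keeps the superseded Part 2 sample sizes (60 + 40, not about 70 + 30) and calls final the cut that the protocol calls a snapshot before a final analysis at 2 years from LPFD

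*SAP*

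**What the plan says.** **Basis of the SAP.** SAP Section 2 says: "This SAP amendment is based on the protocol amendment 3 dated June 3, 2017". SAP Section 5.5, which the version history lists as new in SAP Amendment 2, begins: "In March 2020, prior to the database release for this study, the World Health Organization (WHO) announced a global pandemic". So SAP Amendment 2 dates from March 2020 or later. The current protocol is Amendment 4, dated 07 August 2018.

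**Planned N.** SAP 2.2, 2.2.2, 5.2.2, 5.2.3 and 7 all use 60 NSCLC and 40 urothelial patients. Protocol 3.1, 3.1.2, 9.2.2, 9.3 and 9.4 use 70 and 30.

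**Precision.** For an ORR of 19%, SAP 5.2.3 gives an 80% interval of 13.3 to 26.3% and a 90% interval of 12.1 to 28.6% at N=60. Protocol 9.3 gives 13.4 to 25.2% and 12.2 to 27.3% at N=70.

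**Analysis points.** SAP 7 says: "A final analysis will be performed when all 60 NSCLC patients and 40 urothelial cancer patients are enrolled and have completed their scheduled tumor assessments". Protocol 9.4 item 3 says: "When all 70 NSCLC patients and 30 urothelial cancer patients are enrolled and have completed their scheduled tumor assessments, another snapshot will be taken". Item 4 adds: "A final analysis will be performed at the end of the study, which will be 2 years from LPFD".

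**ORR summaries.** Among the summaries at the snapshot, Protocol 9.4 item 3 lists "ORR, the proportion of patients who achieved CR or PR, by week 16 and the 95% confidence interval for ORR", with DCR over the same window. It also lists tumor response at each assessment and best overall response over all assessments. SAP 6.2.3 has ORR by visit and "Best overall response of CR, PR, and CR+PR, separately for RECIST 1.1 and irRECIST". It gives no week-16 summary. SAP 5.3.2 makes DCR in Part 2 optional.

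**The concern.** The SAP was reopened after the protocol had moved to about 70/30, and it still carries the earlier numbers. Three things follow for anyone who programs from it.

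- The sample-size and precision statements describe a design that is no longer planned.
- The trigger for the only analysis the SAP calls final requires 40 urothelial patients, while the current protocol plans about 30. As written, the trigger would not be met by enrolling to the protocol.
- The SAP names no analysis at 2 years from LPFD. Yet SAP 3.2 keeps the proportion of patients alive at 2 years as a Part 2 secondary endpoint. The protocol's final analysis falls when the last patient dosed reaches 2 years. A cut before that date would rest the 2-year estimate on less follow-up.

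ORR is a Part 2 primary endpoint, so the two documents should also agree on which ORR summaries are produced. The protocol's week-16 figures for ORR and DCR are missing from the SAP.

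**Working it through.** **1. Reproduce each document's own intervals.** Inputs: ORR 19% and N=60 (SAP 5.2.3); ORR 19% and N=70 (Protocol 9.3). Neither document names the interval method. The Wilson score interval reproduces both:

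centre = (p + z²/2n) / (1 + z²/n); half-width = z·√[p(1−p)/n + z²/4n²] / (1 + z²/n), with z = 1.2816 (80%) and 1.6449 (90%).

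| Case | Level | Computed | Stated |
|---|---|---|---|
| N=60, p = 0.19 | 80% | 13.37 to 26.28 | 13.3 to 26.3 (SAP) |
| N=60, p = 0.19 | 90% | 12.08 to 28.60 | 12.1 to 28.6 (SAP) |
| N=70, 13/70 = 18.6% | 80% | 13.36 to 25.22 | 13.4 to 25.2 (protocol) |
| N=70, 13/70 = 18.6% | 90% | 12.15 to 27.33 | 12.2 to 27.3 (protocol) |

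All limits agree within 0.1 point. Each document's arithmetic fits its own N, so the disagreement is about N and not about calculation.

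**2. Size of the NSCLC difference.** The 90% width at N=60 is 28.6 − 12.1 = 16.5 points. At N=70 it is 27.33 − 12.15 = 15.2 points. Part of that gap comes from 13/70 being slightly below 19%. With p held at 0.19, the N=70 interval is 12.50 to 27.81, a width of 15.3, so the difference due to N alone is about 1.2 points.

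**3. Size of the arm differences.** NSCLC: (70 − 60)/60 = 17% more than the SAP states. Urothelial: (40 − 30)/40 = 25% fewer. Total: 60 + 40 = 70 + 30 = 100.

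**4. Urothelial precision, for illustration only.** Neither document gives a planning ORR for this arm, so 10%, 20% and 30% are assumed. SAP 5.3.2 specifies exact 95% intervals (Clopper-Pearson used here).

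| Assumed ORR | N=40: interval (width) | N=30: interval (width) |
|---|---|---|
| 10% | 2.8 to 23.7 (20.9) | 2.1 to 26.5 (24.4) |
| 20% | 9.1 to 35.6 (26.6) | 7.7 to 38.6 (30.9) |
| 30% | 16.6 to 46.5 (30.0) | 14.7 to 49.4 (34.7) |

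The interval is about 3.5 to 4.7 points wider at N=30.

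**5. Analysis points side by side.** The trigger is the same in substance in SAP 7 and Protocol 9.4 item 3: everyone enrolled and scheduled tumor assessments done. The SAP calls that point final. The protocol calls it a snapshot and lists a separate final analysis.

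**6. Can the time between the two cuts be sized?** Taking 2 years as 104 weeks after LPFD:
- assessments complete at week 16: 104 − 16 = 88 weeks;
- complete at week 24, one further 8-weekly scan for confirmation: 104 − 24 = 80 weeks;
- scans followed to end of trial: 0 weeks. Protocol 7.4 allows this for patients who stop treatment without progression: "a tumor assessment will be performed every 12 weeks until disease progression by irRECIST, initiation of a new anti-cancer treatment, or end of trial".

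The documents do not choose among these readings.

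**7. ORR summaries compared.** By-visit response and best overall response without a week limit appear in both Protocol 9.4 and SAP 6.2.3. ORR and DCR by week 16 appear only in the protocol.

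**The case against.** The case for leaving this alone is that it is housekeeping. The SAP openly states that it rests on Protocol Amendment 3, so the N mismatch is a traceable version lag. Both documents let the SAP modify the protocol's plans. The arm sizes are mostly described as approximate and may change after the early look. Reported proportions will use the patients actually enrolled. Both documents size the urothelial arm to expand the safety database and not for precision. The protocol itself sets the later final analysis, and the SAP already defines OS and gives the Kaplan-Meier method, so only a timing statement is missing.

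Most of this stands, and it limits the size of the point. It does not make the SAP text right: a superseded N, interval and trigger remain in a document amended in 2020 or later.

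Three stronger readings may tempt a reader, and the documents do not support them.

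- *That the SAP version history shows an undeclared departure from the protocol.* It records changes between SAP versions. Text carried over unchanged would not appear there, so the history cannot show whether that text was a deliberate choice. Nor do the documents show whether the label for the cut comes from the Amendment 3 basis.
- *That only the SAP lets the follow-up behind ORR depend on the cut.* Protocol 9.4 item 3 also lists best overall response across all assessments. What remains is the omission of the week-16 summaries.
- *That the SAP brings the final analysis forward by 80 to 88 weeks.* That range assumes a meaning for the completion of scheduled assessments that neither document gives. The gap could also be zero.

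**Conclusion.** The point holds as an inconsistency between the current texts of the two documents. The SAP's Part 2 sample sizes, its N=60 precision statement and its final-analysis trigger do not match the current protocol. It schedules no analysis at 2 years from LPFD and omits ORR and DCR by week 16.

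The consequence is modest. There is no hypothesis test in Part 2, so no error rate or power is affected, and the total is unchanged. The NSCLC interval differs by little more than a point in width. The clearest numerical difference is the urothelial arm, which is 25% smaller than the SAP states; the interval widths shown for that arm depend on assumed response rates. The interval between the two cuts is an ambiguity and should not be quoted as an effect.

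The dating of SAP Amendment 2 to March 2020 or later is inferred from its COVID-19 section. The Wilson method is inferred from agreement with the stated limits.

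**What to change.** In the SAP:

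- Base the document on Protocol Amendment 4 (Section 2 and reference 1).
- Change 60/40 to about 70/30 in 2.2, 2.2.2, 5.2.2, 5.2.3 and 7.
- In 5.2.3, replace the N=60 intervals with the protocol's N=70 ones: 80% 13.4 to 25.2%, 90% 12.2 to 27.3%.
- In 7, call the full-enrolment cut a snapshot, and add a final analysis at end of study, 2 years from LPFD.
- Add the protocol's ORR and DCR by week 16, with 95% intervals, to the Part 2 efficacy analyses.

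The cost is SAP wording and the programming of summaries the protocol already requires. No patients, visits or scans are added. The differing Part 1 maximum (n=60 in Protocol 9.2.1, about 40 in Protocol 3.1.4) is a separate matter within the protocol and is not settled by these changes.
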